Intervention Pilot Test. We will recruit 60 people living with HIV who are not virally suppressed and their 60 treatment partners in 1 matched-clinic pair (30 dyads/clinic) in Gaborone, Botswana. We will obtain updated data on 7 satellite clinics in the Greater Gaborone area, and match satellite clinics on number and type of staffing, number of patients total, and number of unsuppressed patients by calculating Euclidean distances between all possible pairs to determine the best (closest) matches, and then selecting one pair of matched intervention and control clinics. Clinics will be randomly assigned to standard of care or a healthcare provider guidance and treatment partner training intervention. In the randomly selected clinic over a 9-month period, (1) clinic healthcare providers will offer guidance around treatment partners to patients who are unsuppressed, in addition to patients who are initiating treatment (although we will only assess intervention effects among those who are not suppressed); and (2) the clinic will offer monthly, open treatment partner training sessions, and request that treatment partners of unsuppressed patients attend ≥ 2 sessions, one within a month after baseline, and one within 3 months after baseline. Patients and treatment partners will be asked to attend two sessions together, so that they can practice role-plays with each other: one within a month after the baseline interview, and one ~ 3 months later (as a booster session). To better fit with clinic flow and the way in which the sessions would ultimately be disseminated and implemented into clinics, the sessions will be open to all treatment partners (regardless of study enrollment) and run monthly for 9 months (during the length of time that the intervention is tested in the clinic). Each one-hour monthly open treatment partner group training session will consist of the same three components: (1) basic HIV treatment education (e.g., names and descriptions of medications and how they work, why adherence is important, how to manage side effects); (2) introduction to Motivational Interviewing (MI), why well-meaning partners can sometimes be unhelpful, how MI strategies (open questions, reflective listening) can be used to better support patients' motivation, and psychoeducation with examples of different types of treatment partner support activities that may be helpful in addition to adherence reminders; and (3) role-plays between patients and treatment partners of different types of challenging situations,

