
All patients and treatment partners will be surveyed at baseline and 3-months post-baseline, and patients' viral loads will be extracted from medical records from baseline to 6-months post-baseline. We will obtain viral load suppression rates for the intervention and control clinic at baseline and 12-months post-baseline. We will conduct an implementation process evaluation of acceptability and feasibility in the intervention clinic, using semi-structured interviews with patients and treatment partners about their experiences with attending the sessions, and healthcare providers about their experiences with intervention implementation, and suggestions for improvement.

Patients will eligible if they (1) are 18 years of age or older; (2) are on ART and initiated ART at least 6 months prior (to have sufficient time to confirm viral load); (3) are not virally suppressed (at least two viral loads ≥ 400 cp/ml within prior 12 months at time of enrollment) and do not show viral resistance in the past 6 months. Viral

load and time from ART initiation will be confirmed with clinic records before enrollment. We will recruit 80 patients (20 per clinic; half men and half women) and their 80 treatment partners. Patients will not be eligible if they screen positive for HIV-related dementia (from clinic records) and if they have not been tested for viral resistance as part of standard of care (all patients failing second-line ART and some patients failing first-line ART are undergo resistance testing). A study nurse will pre-screen patient charts and place study fliers in eligible patients' charts to remind providers to mention the study during the appointment. Interested patients will be told that they can meet with an interviewer in a private clinic space before or after the appointment or at another convenient time for an eligibility screening. Participants can be interviewed immediately after the screening or make an appointment for another time by phone or in person.

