Treatment partners will be eligible if they (1) are 18 years-old or older and (2) were selected to be the PLWH's treatment partner. Based on our pilot, we expect that some treatment partners will also be HIV-positive, and if so, patients and treatment partners may select each other as their treatment partners. For the purposes of study design, we will consider the first patient recruited to be the patient, and the patients' treatment partner to be the treatment partner (regardless of whether the treatment partner is also a patient). After patient and treatment partner participants in the intervention clinic complete the baseline interview, they will be asked to attend the next treatment partner training session (in the next month after the baseline interview), as well as in three months.

STATISTICAL ANALYSIS PLAN

Consistent with R34 guidelines, our primary purpose is to collect preliminary data on feasibility, acceptability, and outcomes; conducting formal tests of outcomes for a measure of effect size is not justified with limited sample size. Thus, the proposed analyses are meant to be exploratory, to help plan for a full RCT. We do not expect to have sufficient statistical power to adequately examine effects. We will calculate descriptive statistics and conduct bivariate analyses of intervention-control differences in change. We will use logistic regression to examine changes in viral suppression (% suppressed at follow-up, % adherent to at least 95% of doses) among enrolled patients in intervention and control clinics. We will use linear regression to examine changes in other survey outcomes (e.g., dyadic relationship support).

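### The suppression analysis names no baseline covariate, so a measured clinic difference in viral-load level would stay in the comparison; the recorded baseline value could be added at little cost

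*Combined protocol and SAP*

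**What the plan says.** The Statistical Analysis Plan is one paragraph. For the binary outcomes it states: "We will use logistic regression to examine changes in viral suppression (% suppressed at follow-up, % adherent to at least 95% of doses". This is to be done among enrolled patients in the intervention and control clinics. No covariate, adjustment set or rule for baseline imbalance is named. The same paragraph says "the proposed analyses are meant to be exploratory, to help plan for a full RCT", and disclaims adequate power.

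The Study Protocol collects the relevant baseline data. Viral "load and time from ART initiation will be confirmed with clinic records before enrollment", and "viral loads will be extracted from medical records from baseline to 6-months post-baseline". In addition, "All patients and treatment partners will be surveyed at baseline and 3-months post-baseline".

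Eligibility requires at least two viral loads of 400 cp/ml or more in the prior 12 months and sets no upper limit. Under Intervention Pilot Test, the plan is to "match satellite clinics on number and type of staffing, number of patients total, and number of unsuppressed patients", with enrolment "in 1 matched-clinic pair (30 dyads/clinic) in Gaborone, Botswana", which makes 60 patients. The eligibility text instead gives 80 patients at 20 in each clinic.

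**The concern.** Patients enter as unsuppressed under the eligibility rule, so a change in suppression is in practice the same thing as suppression status at follow-up. Speaking of changes therefore does not adjust for how far above 400 cp/ml a patient started. Someone just above the threshold and someone far above it count alike.

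The design does not close the gap either. Allocation is by clinic, with one clinic per arm, so there is no averaging over clinics. The matching variables are counts of staff and patients. Two clinics with the same number of unsuppressed patients can differ in how high those patients' viral loads are.

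If baseline viral load predicts later suppression, a clinic difference in its level would appear in the unadjusted comparison as part of the apparent intervention effect. The result is meant to inform a larger trial, and the covariate that would remove this measured part is already in the records.

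**Working it through.** The documents give no suppression rate, effect size or power, so there is no figure in the plan to reproduce. Apart from the 30 per clinic, every input below is an assumption.

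**Inputs.** 30 patients per clinic and one clinic per arm (Intervention Pilot Test). Assumed: no intervention effect; 30 to 50% suppressed at follow-up; an odds ratio of 1.5 to 3 for suppression per SD lower log10 viral load; an ICC of 0, 0.02 or 0.05 for baseline log10 viral load.

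**Step 1: sampling SE of the unadjusted risk difference.** SE = √(2p(1−p)/30). This gives 11.8 points at p = 0.3, 12.65 at 0.4 and 12.9 at 0.5.

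**Step 2: effect of a given gap.** Let logit p(x) = a − ln(OR)·x, with x normal with SD 1 and centred at ± gap/2 in the two clinics, and a set so that mean suppression over both clinics equals the assumed rate. With no intervention effect:

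- a gap of 0.25 SD gives a difference of 2.1 to 5.5 points;
- a gap of 0.5 SD gives 4.1 to 11.0 points.

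The SD of the observed clinic gap is √(2(ICC + (1−ICC)/30)) = 0.258, 0.325 and 0.404 at ICC 0, 0.02 and 0.05. A gap of at least 0.5 SD then has probability 5%, 12% and 22%.

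**Step 3: what is additional to the sampling SE.** At ICC 0 the gap is chance, and its contribution is already inside p(1−p). Only a true clinic-level component adds error. At p = 0.4, a gap of 0.25 SD gives 2.34 points at OR 1.5 and 5.31 at OR 3, so the risk changes by b = 2.34/0.25 = 9.4 to 5.31/0.25 = 21.2 points per SD. The total SE is approximately √(12.65² + b²·2·ICC):

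- ICC 0.02: √(2·0.02) = 0.20, so the added term is 1.87 to 4.25 points and the total SE is 12.8 to 13.3;
- ICC 0.05: √(2·0.05) = 0.316, so the added term is 2.96 to 6.71 points and the total SE is 13.0 to 14.3.

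The inflation runs from 12.79/12.65 = 1.01 to 14.32/12.65 = 1.13.

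**Step 4: what adjustment buys.** Simulation with 30 per clinic, p = 0.4, no effect and no clinic-level component, 4,000 runs per odds ratio:

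| OR per SD | Variance of standardised risk difference ÷ unadjusted | Mean SE of log OR, adjusted (unadjusted 0.538) |
|---|---|---|
| 1.5 | 0.989 | 0.559 |
| 2 | 0.905 | 0.580 |
| 3 | 0.833 | 0.619 |

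A separate calculation used a different scale: SD 0.8 log10, odds ratios of 0.70, 0.50 and 0.35 per log10, 30% or 50% suppressed in the control clinic, and clinic differences of 0, 0.25 and 0.5 log10. With baseline log10 viral load in the model, the median clinic odds ratio was 0.97 to 1.04 in every scenario. Without it, the odds ratio implied by the difference was 1.09 to 1.26 at 0.25 log10 and 1.19 to 1.58 at 0.5 log10.

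**Step 5: room for the covariate.** At 30 to 50% suppressed, 60 patients give 18 to 30 suppressed, if all follow-up viral loads are available. That supports two terms, clinic and baseline viral load.

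**Step 6: the sample size conflict.** 2 × 30 = 60 agrees with one matched pair. 80/20 = 4 implies four clinics. If that meant two clinics per arm, there would be 40 patients per arm, and the step 1 SEs would be √(2p(1−p)/40) = 10.2 to 11.2 points.

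**The case against.** The strongest reply is that this is a one-paragraph plan for an underpowered pilot, which itself says that formal outcome tests for an effect size are not justified. A 95% interval for the risk difference is about ±25 points (1.96 × 12.65) with or without the covariate. The main limitation, one clinic per arm, is untouched by adjustment, and an adjusted result may look better controlled than it is. This stands. It limits the weight of the point and is why the limitation should be printed beside the result. It is not a reason to leave a recorded prognostic value unused.

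Four stronger readings are tempting, and the documents do not support them.

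- A reader might set the 4 to 11 points of step 2 beside the 12 to 13 point SE as a separate error. A chance gap is already counted in that SE; only the inflation in step 3 is additional.
- A reader might infer that the SAP rules out covariates. It is silent, and it lists regression apart from the bivariate analyses.
- A reader might infer that the pilot estimate will set the effect size of the full trial. The SAP says only that the analyses help to plan it.
- A reader might extend the point to the survey outcomes, where the plan is "We will use linear regression to examine changes in other survey outcomes (e.g., dyadic relationship support", and ask for a baseline-adjusted estimate instead. An analysis of change already uses the baseline value. If a baseline gap is a stable clinic difference, the change score is unbiased and the baseline-adjusted estimate is not; if the gap is chance, the reverse holds given that gap. With one clinic per arm neither is clearly better, so no change is asked for there.

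One detail also needs care. Eligibility asks for two values of at least 400 cp/ml within 12 months, not that the latest value be one of them. Baseline status is therefore not strictly fixed, which does not weaken the case for using the last recorded value.

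**Conclusion.** The point holds, with modest weight, for the suppression model and, where baseline adherence is measured, for the adherence model. That no covariate is named, that baseline viral load is available, and that matching does not address its level all follow from the documents. The size does not: it depends on the assumed suppression rate, prognostic strength and ICC. On those assumptions, leaving out the covariate costs up to about 17% of the variance of the risk difference (ratio 0.99 to 0.83). If there is a true clinic-level difference, the unadjusted SE at 40% suppressed is about 1 to 13% larger than the sampling SE. The consequence is a somewhat noisier planning estimate, not a false confirmatory claim.

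Adjustment removes only measured patient-level differences. It cannot separate clinic from treatment here. The contradiction over the number of patients and clinics is in the documents and does not depend on any assumption.

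**What to change.** 1. Add the last log10 viral load at or before enrolment to the logistic model for suppression. Add baseline adherence to the adherence model where the baseline survey measures it.
2. Report each adjusted result as a standardised risk difference with an interval, and keep the unadjusted result alongside.
3. State that the adjustment covers only measured patient-level differences, and that clinic and treatment cannot be separated with one clinic per arm. The interval then describes variation between patients, not between clinics.
4. Reconcile 60 patients at 30 per clinic in one matched pair with 80 patients at 20 per clinic.

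The cost is one covariate per model, a few lines of SAP text and one more column of results. No new viral-load data are needed. The downsides are one more term in a small model and a slightly larger SE on the log-odds-ratio scale, which is why the risk difference is the better scale to report.

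### With one clinic per arm, the intervention effect cannot be separated from the clinic effect, the SAP does not say so, and the stated patient and clinic counts conflict

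*Combined protocol and SAP*

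**What the plan says.** **Design.** The Intervention Pilot Test paragraph of the Study Protocol recruits 60 patients and their 60 treatment partners "in 1 matched-clinic pair (30 dyads/clinic) in Gaborone, Botswana". The pair is found by matching seven satellite clinics on staffing, total patients and number of unsuppressed patients, "then selecting one pair of matched intervention and control clinics". The unit of randomisation is the clinic: "Clinics will be randomly assigned to standard of care or a healthcare provider guidance and treatment partner training intervention".

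**Clinic-level data.** The assessments paragraph also speaks of one clinic per arm: "We will obtain viral load suppression rates for the intervention and control clinic at baseline and 12-months post-baseline".

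**Conflicting count.** The eligibility and recruitment paragraph says: "We will recruit 80 patients (20 per clinic; half men and half women) and their 80 treatment partners".

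**Analysis.** The Statistical Analysis Plan has bivariate comparisons of change between arms, logistic regression for suppression and for adherence of at least 95% "among enrolled patients in intervention and control clinics", and linear regression for other survey outcomes. It describes the work as exploratory and as preparation for a full RCT. It expects too little power and says that "conducting formal tests of outcomes for a measure of effect size is not justified with limited sample size". It does not discuss clustering or the coincidence of arm and clinic.

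**The concern.** When each arm is one clinic, any difference between the arms is also a difference between two clinics in staff, patients and local trends over the study period. A patient-level regression assigns all of it to the intervention term, and its ordinary standard error contains no between-clinic variance.

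The SAP's caveats concern size and power, which suggests that a larger sample would resolve the difficulty. Here it would not. What is at stake is how the results are used: the aims include preliminary effects on viral suppression, and the analyses are meant to inform a full trial. An ordinary difference between two clinics could be carried forward as an intervention signal, and an interval taken from standard regression output would look tighter than it should for that purpose.

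The count conflict bears directly on this, because the number of clinics decides whether there is any between-clinic information at all.

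**Working it through.** **1. Counts.**
- Pilot test paragraph: 2 clinics × 30 = 60 patients, which reproduces the stated 60.
- Recruitment paragraph: 80 / 20 = 4 clinics. Two clinics at 20 each would give only 40.
- The two statements cannot both describe the same study.

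**2. Aliasing with one clinic per arm.**
- A model with intercept, intervention and clinic has 3 columns of rank 2. Removing the intervention column leaves rank 2, so the two terms are identical and no clinic term can be added.
- Between-clinic degrees of freedom within arm: 2 clinics − 2 arms = 0.
- Analysing change does not help. With intercept, clinic, time, intervention × time and clinic × time there are 5 columns of rank 4.
- None of this depends on an assumed ICC.

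**3. What change scores achieve.**
- Survey outcomes are measured at baseline and 3 months. Stable clinic differences cancel; clinic-specific trends remain.
- Every enrolled patient is unsuppressed at entry, by the eligibility criteria. For suppression, the comparison of change is therefore simply the follow-up difference between two clinics.

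**4. Illustrative size.** The documents give neither an ICC nor an expected suppression rate. Assumptions: p = 0.30 suppressed in each arm; ICC 0 to 0.10. From the pilot test paragraph: m = 30 per clinic.
- Ordinary standard error of the difference: sqrt(2 × 0.30 × 0.70 / 30) = sqrt(0.014) = 0.118.
- Ordinary 95% half-width: 1.96 × 0.118 = 0.232.
- Design effect: DE = 1 + (m − 1) × ICC. The half-width is multiplied by sqrt(DE).

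| Assumed ICC | DE | sqrt(DE) | Half-width (points) |
|---|---|---|---|
| 0 | 1.00 | 1.00 | 23 |
| 0.01 | 1.29 | 1.14 | 26 |
| 0.05 | 2.45 | 1.57 | 36 |
| 0.10 | 3.90 | 1.97 | 46 |

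**5. Why more patients do not cure it.** The effective number of independent patients per clinic is m / DE, with ceiling 1/ICC as m grows. At ICC 0.05:
- m = 30: 30 / 2.45 = 12.2
- m = 60: 60 / 3.95 = 15.2
- ceiling: 1 / 0.05 = 20

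**6. If there are four clinics.** With two matched pairs, a cluster-level analysis has 2 − 1 = 1 df (two-sided 5% t critical value 12.71), or 4 − 2 = 2 df (4.30) if the matching is ignored. Aliasing is no longer complete, but inference remains very weak.

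**The case against.** The strongest reply is that the SAP already disowns most of the possible misuse. It calls the analyses exploratory, expects inadequate power and says that formal tests for an effect size are not justified. This stands. A reader might infer from the design effects that the trial plans an invalid test with an inflated false-positive rate. The documents do not support that: the SAP commits to no p-value and no interval. Nor does it ignore clinics, since it names intervention and control clinics as the groups compared. With one clinic per arm no clinic term could be fitted in any case, so what is missing is a statement, not a model term.

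It can also be said that limited sample size, in a clinic-randomised pilot, might mean few clinics. The sentence does not say so, and a reader would more naturally take it to mean patients.

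Matching, which uses total patients and number unsuppressed, may make the relevant ICC smaller than the larger values shown, and change scores remove stable differences in survey outcomes. Both points stand as reasons to treat the table as a range. Neither removes nor measures clinic-specific change. The clinic-wide suppression rates at baseline and 12 months give useful context, but they again compare one clinic with one.

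A reader might also infer that each clinic's own interval is too narrow. That does not follow: an ordinary interval is adequate for describing one clinic's own proportion. Between-clinic variance matters when the difference between arms is attributed to the intervention or generalised to other clinics.

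**Conclusion.** The concern holds as a missing limitation statement together with a real inconsistency in the counts. If there is one clinic per arm, as the pilot test and assessments paragraphs indicate, the confounding of intervention with clinic is complete, and that conclusion needs no assumption. It is conditional on that reading: the 80-patient statement would imply four clinics, where aliasing is not complete.

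The size of the effect on precision is only illustrative. At an assumed 30% suppression in each arm, the half-width for the between-arm difference goes from about 23 points at ICC 0 to 46 at ICC 0.10. It is minor at very small ICCs: at 0.005, DE = 1 + 29 × 0.005 = 1.145 and the standard error grows by a factor of only 1.07.

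A stronger reading, that the pilot's planned analysis is faulty or its feasibility and acceptability aims are undermined, is not supported. The SAP's exploratory framing is appropriate; its stated reasons are incomplete.

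**What to change.** 1. **Reconcile the counts.** State one sample size and one number of clinics throughout (60 at 30 per clinic, or 80 at 20 per clinic).
2. **With one clinic per arm, state the limitation in the SAP.** Say that intervention and clinic effects are inseparable and that more patients in these clinics would not change this. Report each clinic's results and the difference descriptively, without between-arm p-values. Do not use the difference as the planning effect size for the full RCT.
3. **If an interval is shown for the between-arm contrast**, either label it as excluding between-clinic variance, or multiply its standard error by sqrt(1 + (m − 1) × ICC) over a stated range of assumed ICCs that includes 0. Intervals for each clinic's own proportion need no inflation.
4. **If there are four clinics in two matched pairs**, remain descriptive, given 1 df (2 if the matching is ignored).

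The cost is SAP wording and a correction of the protocol counts; no new data are needed. The downside is wider or labelled intervals and no between-arm p-values, which fits the SAP's own exploratory purpose.
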